#### 1 INTRODUCTION

This document describes the statistical analyses and data presentations to be performed for Clovis Oncology protocol CO-1686-019 "A Phase 2, Open-Label, Multicenter, Safety and Efficacy Study of

5 of 17

Oral CO-1686 as 2nd Line EGFR-Directed TKI in Patients with Mutant EGFR Non-Small Cell Lung Cancer (NSCLC) with the T790M ".

This version of the Statistical Analysis Plan (SAP) provides detail outlines of the statistical analyses that will be presented for the MAA and NDA, which were originally outlined in the original protocol dated 17th of Feb, 2014, and Amendment 1 dated 1st of May 2014, Amendment 2 dated 9th of May 2014, and Amendment 3 dated 27th of Oct 2014.

All statistical analyses detailed in this SAP will be conducted using SAS® Version 9.3.

#### 2 OVERALL STUDY DESIGN AND OBJECTIVES

## 2.1 Trial Design and Study Procedures

This is a Phase 2, single arm, open-label, multicenter study evaluating the safety and efficacy of CO-1686 administered orally twice daily to patients with previously treated mutant EGFR NSCLC whose tumor harbors the T790M resistance mutation. The central laboratory will confirm that the patient's tumor harbors the T790M mutation using biopsy material obtained from either primary or metastatic tumor tissue within 28 days of dosing with study drug and after progression on EGFR directed therapy.

CO-1686 will be administered to patients twice daily. Patients will take CO-1686 with a meal or within 30 minutes after a meal. Treatment with CO-1686 is continuous. Each 28 day period of treatment will represent one cycle, with dosing initiated on C1 D1. No dose escalation beyond the starting dose is allowed.

Patients will undergo serial assessments for anti-tumor efficacy, drug safety, and patient reported outcomes (see Section 9 of the Protocol). Sparse blood sampling for population PK analyses will be conducted in all patients treated with CO-1686. Serial blood sampling for longitudinal quantitative assessment of ctDNA will be conducted. Central laboratories will be used for hematology and chemistry, as well as for ECG interpretation.

Tumor scans will be acquired by the investigative site and evaluated locally for patient treatment decisions; however, copies of tumor scans will be sent to a independent radiological review (IRR) vendor. Protocol-specified treatment will continue until there is RECIST or clinical tumor progression or unacceptable toxicity as assessed by the investigator. Following disease progression on CO-1686 and discontinuation of protocol-specified treatment, patients who provide additional consent will undergo tumor biopsy before subsequent-line therapy is initiated. After discontinuation of protocol-specified treatment, subsequent anticancer therapy will be recorded.

All patients should return to the clinic for end-of-study assessments 28 (±7) days after the last dose of oral CO-1686 has been administered. The trial will be completed when all cnrolled patients have discontinued treatment in this protocol and completed the end-of-study follow-up visit.

All patients will be followed at approximately two monthly intervals to monitor survival status and subsequent NCSLC cancer therapy until death or sponsor decision, whichever comes first.

After discontinuation of protocol-specified treatment, subsequent anticancer therapy use will be recorded.

# 2.2 Sample Size used

Approximately 125 patients are planned to be enrolled under the protocol and subsequent Amendments for the MAA and NDA.

For the initial MAA and NDA submissions all patients enrolled in this trial by the 31st of December 2014 with a data cutoff date of April 2015 will be used for both efficacy and safety conclusions. The efficacy and safety profile for CO-1686 will be established by the combined patients treated in this study and Phase 1 study, CO-1686-008.

Confidential 7 of 17

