The most frequently reported AEs ($\geq 20\%$ of patients), regardless of causality or severity, were nausea (40%); AEs associated with blood glucose increases (39%; including Medical Dictionary for Regulatory Activities [MedDRA] preferred terms [PTs] blood glucose elevated, glucose tolerance impaired, and hyperglycemia); fatigue (26%); diarrhea (26%); and decreased appetite (22%).

AEs considered to be related to rociletinib and reported in $> 5\%$ of patients overall are summarized by system organ class (SOC), PT, and dose level in [Table 3-2](#). The most frequently reported treatment-related AEs ($\geq 20\%$ of patients), regardless of severity, were nausea (28%); increased blood glucose, combined terms as in the previous paragraph (33%), and fatigue (20%).

The majority of AEs have been mild or moderate in severity. Rociletinib selectively inhibits mutant EGFR, and as expected, the syndrome of dose related WT-driven rash and diarrhea has not been observed. All reported events of diarrhea were either Grade 1 or Grade 2.

The most common skin reaction reported in patients treated with EGFR-TKIs is a follicular acneiform eruption. In Study CO-1686-008, rash, irrespective of causality, was reported infrequently (overall 6 patients [4%]) and all events were mild. In Study CO-1686 008, only 1 report of dermatitis acneiform and 1 report of follicular rash have been reported to date.

There have been 2 AEs of pneumonitis and 1 SAE of pneumonitis, all assessed as related to rociletinib by the investigator. Patients recovered after steroid therapy, and patients were not rechallenged with rociletinib.

Electrocardiogram (ECG) Changes

Rociletinib exposure is associated with QT interval corrected for heart rate (QT_c) prolongation. The effect takes several days to develop, and is not seen on Day 1 of therapy. Patients with low baseline resting heart rates appear to be at a higher risk for QT_c prolongation during treatment with rociletinib. Typically, the abnormality is evident by Day 15 of therapy, and the increase remains stable with continued dosing.

Prolonged QT_c is managed effectively by dose reduction.

Table 3-2: Treatment-related Adverse Events Reported in at Least 5% of Patients in Study CO-1686-008

SOC PT	< 900 BID FB (N = 38)	900 BID FB (N = 19)	500 BID HBr (N = 18)	625 BID HBr (N = 17)	750 BID HBr (N = 50)	1000 BID HBr (N = 6)	Overall (N = 148)
Number of Patients with at Least 1 Treatment-related TEAE							

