CO-1686 causes hyperglycemia in some patients secondary to inhibition of the insulin-like growth factor 1 receptor (IGF-1R) and insulin receptor (IR) kinases by a metabolite. Therefore, some patients will require addition of a glucose lowering medication and patients with pre-existing diabetes may require more frequent monitoring and/or adjustments of diabetic medication. Clinical experience with CO-1686 suggests hyperglycemia generally occurs within the first 3 weeks of treatment, leading to the need for more intensive glucose monitoring during the first several weeks of the study. In Phase 1/2 clinical trial experience, increased nausea and vomiting, and decreased appetite, diarrhea, muscle cramps and fatigue have been reported in patients with hyperglycemia. Such patients must be closely monitored including assessment of fasting glucose levels and early initiation of anti-hyperglycemic therapy. As CO-1686-induced hyperglycemia is mediated through insulin resistance, agents that suppress glucose synthesis (metformin), increase sensitivity to insulin (glitazones) or increase glucose excretion (sodium-glucose cotransporter 2 [SGLT2] inhibitors) are expected to be more effective than those that increase plasma insulin (sulphonylureas or exogenous insulin). Metformin has been

used most frequently in CO-1686 clinical studies and is, therefore, recommended as the initial agent to manage hyperglycemia in patients with normal renal function. In addition, preliminary data from the ongoing Study CO-1686-008 suggest that starting metformin at the same time CO-1686 therapy is initiated may prevent the development of CO-1686-induced hyperglycemia. For all patients, irrespective of whether they are receiving metformin prophylactically or therapeutically, glucose monitoring should be conducted according to the following schedule:

- Fasting glucose will be measured at the following visits: Screening, C1D1, C1D4 (± 1 day), C1D8 (± 1 day), C1D15 (± 1 day), C2D1, C2D15 (± 1 day), C3D1, C4D1, C5D1, CND1... and End-of-Treatment Visit.

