#### 4 ANALYSIS POPULATIONS

**Safety Population**—all patients who have received at least one dose of CO-1686.

Efficacy Population—all patients who received at least one dose of CO-1686, have at least one measureable tumor lesion at baseline, and have at least one post-baseline tumor assessment or patients who died before first post-baseline scan. Due to that the efficacy is both assessed by the investigator and the independent radiologist there will be two different efficacy populations:

- Investigator Efficacy-Evaluable Population Flag
- IRR Efficacy-Evaluable Population Flag

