# 12 SUMMARY OF CHANGES FROM PROTOCOL SPECIFIED ANALYSES

Due to the accelerated approval strategy with the NDA submission, the data presented in the NDA will be a subset of the overall study with patients enrolled up to the 31st of December with a visit data cutoff of 29 April 2015. Hence, due to the ongoing nature of the data in this trial the following analyses will not be performed at the time of the NDA version but will be performed when the study is completed:

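### The submission safety tables use the efficacy enrolment cut of 31 December 2014, so events already observed by 29 April 2015 in later enrollees go uncounted, and no safety-specific reason is given

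*SAP*

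**What the plan says.** SAP 1 describes this SAP version as giving the "detail outlines of the statistical analyses that will be presented for the MAA and NDA". SAP 2.2 then sets the data for the first filings: "all patients enrolled in this trial by the 31st of December 2014 with a data cutoff date of April 2015 will be used". The same sentence makes clear that the set serves safety as well as efficacy ("will be used for both efficacy and safety conclusions"). Its next sentence says that the efficacy and safety profile will come from this study combined with CO-1686-008.

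SAP 12 repeats the restriction: "the data presented in the NDA will be a subset of the overall study with patients enrolled up to the" 31 December enrolment date. It gives the visit cutoff as 29 April 2015 and the accelerated approval strategy as the reason. It postpones PFS, OS, DCR, quality of life and the exploratory objectives to study completion. Safety in patients enrolled after the cut is not on that list.

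SAP 4 defines the safety population as "all patients who have received at least one dose of CO-1686", and SAP 11 bases the safety analyses on it. Neither section mentions an enrolment date.

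On timing of toxicity, Protocol 7.4 states: "Clinical experience with CO-1686 suggests hyperglycemia generally occurs within the first 3 weeks of treatment". Protocol 3.4.1.1 says of QTc prolongation: "Typically, the abnormality is evident by Day 15 of therapy".

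**The concern.** An enrolment cut well before the data cutoff suits response and duration of response, because a patient needs at least one post-baseline scan (every 8 weeks) and then further follow-up. The same argument does not carry over to toxicity that appears in the first two or three weeks. By the plan's own timing, most patients enrolled between the two dates could have passed through the hyperglycemia and QTc onset periods before the cutoff.

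What is at stake is completeness more than precision. A death, an SAE, or a Grade 3 hyperglycemia or QTc event in a patient enrolled in, say, February 2015 could be recorded before the cutoff and still appear in none of this study's submission safety tables. In addition, SAP 4 and 11, read alone, give a different denominator from SAP 2.2 and 12, and no cross-reference tells the programmer or the reader which applies.

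**Working it through.** There is no design figure to reproduce here; the point rests on dates.

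**Inputs.** Enrolment cut 31 December 2014 (SAP 2.2). Data cutoff 29 April 2015 (SAP 12). Onset by Day 15 for QTc (Protocol 3.4.1.1) and within 3 weeks for hyperglycemia (Protocol 7.4). Planned enrolment about 125 (SAP 2.2). CO-1686-008 had treated 148 patients by 4 June 2014 (Protocol 3.4.1).

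**Length of the window.** 29 April 2015 minus 31 December 2014 = 119 days = 17.0 weeks = 4.25 cycles of 28 days.

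**Who had passed the onset period by the cutoff.**
- Day 15 reached: first dose on or before 15 April 2015, which is 105 of the 119 dates (88%).
- 21 days observed: first dose on or before 8 April 2015, which is 98 of the 119 dates (82%).

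These are shares of calendar dates, not of patients. The scheduled checks fall inside the same periods: fasting glucose on Cycle 1 Days 4, 8 and 15 (Protocol 9.5.1.2) and an ECG on Cycle 1 Day 15 (Protocol 9.5.1.4).

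**How many patients.** The documents give neither an accrual curve nor a count. If accrual were uniform up to the cutoff, the share enrolled after 31 December would depend on the start date:
- start 17 February 2014 (date of the original protocol, SAP 1): 119/436 = 27%;
- start 1 August 2014 (assumed): 119/271 = 44%.

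Both are illustrations. Late accrual may have been much lower, so the table below assumes that 10% to 50% of 125 patients (12 to 62) were enrolled after the cut. The row with 80 patients corresponds to 36% excluded (45/125), inside the 27%-44% range.

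**Precision, this study alone and pooled.** The chance of at least one event with an assumed true rate of 2% is 1 − 0.98^n. With zero events, the one-sided 95% upper bound is 1 − 0.05^(1/n). The pooled columns add only the 148 CO-1686-008 patients known by June 2014.

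| n, this study | P(≥1 event) | Zero-event bound | n, pooled | P(≥1 event) | Zero-event bound |
|---|---|---|---|---|---|
| 125 (none excluded) | 92.0% | 2.4% | 273 | 99.6% | 1.1% |
| 113 (12 excluded) | 89.8% | 2.6% | 261 | 99.5% | 1.1% |
| 80 (45 excluded) | 80.1% | 3.7% | 228 | 99.0% | 1.3% |
| 63 (62 excluded) | 72.0% | 4.6% | 211 | 98.6% | 1.4% |

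In the pooled columns the chance of seeing the event falls by at most 1 percentage point across this range. In this study's own tables the loss could be visible, but its size depends entirely on the unknown number excluded.

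**Is the gap covered elsewhere?** SAP 12 lists what is postponed to study completion, and safety is not listed. SAP 11 describes no separate listing or table for later enrollees. The only reason given, the accelerated approval strategy and the ongoing nature of the data, concerns maturity of follow-up and does not address events of early onset.

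**The case against.** The strongest reply is that the restriction is declared, not hidden. This SAP version covers the MAA and NDA only, SAP 2.2 speaks of the initial submissions, and SAP 12 announces the subset in the section on departures from the protocol. A population definition normally operates within the declared data set. That stands. A reader might infer that SAP 2.2 contradicts SAP 4, or that later patients' safety is never to be analysed; the documents support neither. What is missing is a cross-reference and a reason specific to safety.

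Second, the cut is by enrolment. A reader might infer that everyone dosed in the last four months is left out. That is wrong: a patient enrolled in December and first dosed in January stays in, and included patients still on treatment contribute data up to the cutoff.

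Third, the number excluded could be small. SAP 2.2 can be read as making the roughly 125 patients the submission set itself, and the safety profile is pooled with CO-1686-008. A claim of materially weaker detection of rare harms is therefore not supported for the pooled conclusions. CO-1686-008 does span several doses and two formulations, and pooling does not bring back this study's later patients.

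Fourth, the SAP's adverse event tables are crude counts and percentages. Adding patients with only days or weeks of exposure can dilute the incidence of later-onset events. The protocol's early-onset statements cover hyperglycemia and QTc only; it makes none for pneumonitis or deaths. If any 500 mg BID (Cohort B) patients had been dosed by the cutoff, one all-dosed column would mix them with 625 mg BID patients, and the SAP does not mention Cohort B. These points are sound. They argue against replacing the 31 December set, but not against showing a second presentation beside it.

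**Conclusion.** The point holds in a limited form. For the initial MAA and NDA, patients enrolled in the 119 days after 31 December 2014 are left out of the safety tables, the reason given does not address safety, and no other section covers them. The real loss is that observed deaths, SAEs and early-onset events in these patients go uncounted in this study's tables.

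The size in patients is unknown. The 27%-44% shares and the table rows rest on assumed accrual and an assumed 2% event rate. For the pooled conclusions the loss of precision is small (99.6% against 99.0% in the row with 80 patients). The onset statements come from the current protocol (Amendment 5), whereas the SAP cites amendments only up to Amendment 3, although the QTc statement sits in a summary of data as of 4 June 2014.

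This is a choice of analysis set, and nothing here bears on dosing or clinical management. It is a cheap improvement, not a flaw that undermines the plan.

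**What to change.** In SAP 2.2 and 12:
- keep the 31 December 2014 set for efficacy and as one safety column;
- add a safety presentation for all patients with at least one dose by 29 April 2015, covering at minimum deaths, SAEs, Grade 3 or greater TEAEs, hyperglycemia and QTc;
- split the added presentation by starting dose and cohort, and show exposure time beside the counts so that short follow-up is visible;
- cross-reference SAP 4 and 11 so that the denominator of each safety table is unambiguous.

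No new assessments are needed: Protocol 10.8 already requires SAE reports within 24 hours, and Protocol 13.5 requires eCRF completion in under 2 weeks. The cost is cleaning and coding the later patients' records and programming the extra tables. The added patients will have shorter follow-up, so their column should not be read as an estimate of later-onset toxicity.

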# 2.3 Study Objectives and Endpoints

#### 2.3.1 Primary Objectives

 To evaluate the antitumor efficacy of oral single agent CO-1686, as measured by objective response rate (ORR), when administered to patients with EGFR-mutated, T790M positive, advanced non-small cell lung cancer (NSCLC) after tumor progression on one previous EGFRdirected TKI

#### 2.3.2 Secondary Objectives

The secondary objectives of this study are:

- To assess secondary measures of clinical efficacy (disease control rate (DCR), duration of response (DR), progression free survival (PFS), overall survival (OS) following CO-1686 treatment
- To evaluate the safety and tolerability of CO-1686
- To determine pharmacokinetics (PK) of CO-1686 using population PK (POPPK) methods and explore correlations between PK, exposure, response, and/or safety findings

#### 2.3.3 Primary Endpoints

 ORR according to Response Criteria in Solid Tumors (RECIST) Version 1.1 as determined by independent radiology review (IRR)

#### 2.3.4 Secondary Endpoints

- DR, DCR and PFS according to RECIST Version 1.1 as determined by IRR
- ORR, DR, DCR and PFS according to RECIST Version 1.1 as determined by Investigator Assessment
- OS
- Treatment emergent adverse events (AEs), laboratory abnormalities and ECG abnormalities
- Plasma PK parameters for CO-1686 based on sparse sampling

#### 3 GENERAL ANALYSIS CONVENTIONS

Quantitative variables will be summarized using descriptive statistics and may also be summarized categorically with frequencies and percentages. For variables registered on a continuous scale, the following will be presented: N, mean, standard deviation, median, minimum and maximum. Categorical variables will be presented using frequencies and percentages.

The Kaplan-Meier methodology will be used to summarize DR, PFS, and OS. If estimable, the 50th (median) together with a 95% Confidence Interval (CI) will be presented. The number of patients with events and the number of censored patients will also be presented.

All data will be used to their maximum possible extent but without any imputations for missing data.

Unless otherwise specified, baseline is defined as the last measurement on or prior to the first day of study drug administration.

#### 4 ANALYSIS POPULATIONS

**Safety Population**—all patients who have received at least one dose of CO-1686.

Efficacy Population—all patients who received at least one dose of CO-1686, have at least one measureable tumor lesion at baseline, and have at least one post-baseline tumor assessment or patients who died before first post-baseline scan. Due to that the efficacy is both assessed by the investigator and the independent radiologist there will be two different efficacy populations:

- Investigator Efficacy-Evaluable Population Flag
- IRR Efficacy-Evaluable Population Flag

#### 5 PATIENT DISPOSITION

The frequency and percentage of patients in each analysis population will be presented. In addition, the number of ongoing patients and the number of patients who have discontinued will be presented, together with the primary reason for discontinuation.

Confidential 10 of 17

#### 6 DEMOGRAPHICS AND BASELINE CHARACTERISTICS

All demographic and baseline characteristics will be summarized for the safety population.

## 6.1 Demographics

The demographic variables will be summarized with frequency tabulations that will focus on identifying the extreme values of the distributions. Descriptive statistics will also be used to summarize the quantitative variables. The demographic variables presented will include age, height, weight, gender, race, and ECOG Performance Status using the following categorizations:

- Age (years):  $\leq 50$ , 51-65, 65-80, 81-95, >95;
- Height (cm):  $\leq 75$ ,  $\geq 75-100$ ,  $\geq 100-125$ ,  $\geq 125-150$ ,  $\geq 150-175$ ,  $\geq 175$ ;
- Weight (kg):  $\leq 50$ , > 50-75, > 75-100, > 100-125, > 125-150, > 150;
- Gender: Male, Female
- Ethnicity: Hispanic or Latino, Not Hispanic or Latino
- Race: American Indian or Alaska Native, Asian, Black or African American, Native Hawaiian or Other Pacific Islander, White, Other
- ECOG Performance Status: 0, 1, 2.

#### 6.2 Baseline Clinical Characteristics

The following variables will be summarized with descriptive statistics and may also be summarized with frequency tabulations, as indicated:

- Time since diagnosis of NSCLC (months):  $\leq 3, \geq 3-6, \geq 6-12, \geq 12-24, \geq 24$ ;
- Baseline laboratory parameters: graded based on CTCAE grading
- T790M status
- Molecular characterization of EGFR mutations.

# 6.3 Medical History

Medical history data will be summarized using frequency tabulations by system organ class and preferred term.

Confidential 11 of 17

## 7 STUDY DRUG EXPOSURE

The following variables will be summarized:

- Number of cycles initiated
- · Number of days of treatment initiated

The number of days of treatment initiated will be investigated by summarizing the number of days from treatment start date to treatment end date +1 or if the subject is ongoing then we use the date of the data cutoff.

#### 8 PRIOR AND CONCOMITANT MEDICATIONS

All concomitant treatments documented during the study treatment period will be summarized with frequency tabulations. Prior/concomitant medication coding will utilize World Health Organization (WHO) Drug version 2015MAR01DDE (Enhanced).

Separate data summaries of prior medications will be provided. Prior medications will be defined as those medications with both a start and a stop date that is before the day of the first dose of study drug administration. If either the start date and/or the stop date of the medication is missing so that it is unclear whether the medication was stopped prior to first dose of study drug administration then the medication will be included in the summary of the concomitant medications.

Confidential 12 of 17

